Other recruitment. Participants will also be recruited from clinic and community flyers, newspaper advertisement, UF HealthStreet, and the UF Pain Research and Intervention Center of Excellence (PRICE), Institute on Aging Pepper Center, and the University of Florida Jacksonville Aging Studies Center Research Participant Recruitment registries.

Screening. All potential participants will undergo an initial phone screening interview, via telephone or in person. We have requested a waiver of written informed consent to retain this information; we will provide verbal consent information and allow participants the chance to ask questions. The initial screening will include questions regarding pain, age, weight, and additional health history information to ensure that no exclusion criteria are present. For participants not affiliated with the University of Florida Health Care system, we will be asking a series of questions to assess any instability of the spine. If instability is determined, the participant must contact their own physician for written permission to partake in the study. If still eligible, participants will be scheduled for an individual in-person baseline assessment during which informed consent will be reviewed, medical and demographic history will be obtained to ensure eligibility, questionnaires will be administered, and a physical performance battery will be conducted to examine lower extremity function. At the completion of the baseline assessment, eligible participants will be scheduled for the intervention program (90 min/session).

Participants. A total of 40 middle-aged and older adults with moderate-to-high impact chronic musculoskeletal pain (e.g., lower back, knee, hip) and overweight/obesity ($BMI \geq 25 \text{ kg/m}^2$) will be targeted. Assuming a 20% attrition rate, an additional 8 subjects will be enrolled, leaving a total of 48 participants to be recruited for study intervention procedures (we anticipate recruiting a total of 60 people to account for screen failures). Participants will still be included if they report the presence of medical pain comorbidities; however, subjects must identify musculoskeletal pain as their primary pain condition.

Inclusion Criteria

- 45-80 years of age
- Have a $BMI \geq 25 \text{ kg/m}^2$
- Endorse pain in the lower back region (i.e., space between the lower posterior margin of the rib cage and the horizontal gluteal fold), knees, or hips

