will complete standardized self-report questions at each intervention phone call on their weekly engagement in pleasant activities, duration of engagement (in minutes), and the level of enjoyment for each activity (completed on a numerical rating scale [NRS] ranging from 0 “none” to 100 “extremely”). The **Meaningful Activity Participation Assessment** (MAPA)¹⁶ is a 28-item checklist reflecting common activities that are meaningful to older adults. Items are rated both for how much time is spent and how meaningful the activities are perceived to be. The **Positive and Negative Affect Schedule** (PANAS)⁶³ is a 20-item scale assessing positive affect (PA) and negative affect (NA). The **Food Pain Coping Questionnaire** is a 2-item scale assessing food use as a coping mechanism for chronic pain. The **World Health Organization Quality of Life-Brief** (WHOQol-Bref)⁵² scale consists of 26 items assessing quality of life over the past week in four domains: physical health, psychological health, social relationships, and environment.

To measure **Ecological Momentary Assessment (EMA) of Pain, Mood, and Physical Activity**, the smartwatch app ROAMM will be installed on commercially-purchased smartwatches (i.e., Apple Watch) to obtain real-time measures of pain intensity, mood, and physical activity.³⁶ Participants will be asked to wear a smartwatch for 7 days at baseline and 7 days at the 4-month time-point, during which they will receive three daily prompts (morning, afternoon, evening) to complete measures of current pain intensity (0 to 10 NRS ranging from none to worst possible) and mood (0 to 10 NRS ranging from extremely negative to extremely positive mood). Participants will also complete nightly prompts as to whether they engaged in a 1) social activity, 2) mind-enriching activity, and 3) exercise (yes or no response). Assessment ratings will be entered by rotating a bezel on the watch interface. Continuous accelerometry data will be collected as a measurement of physical activity (average minutes spent per day; collected at 15 Hz).

Statistical Methods. To account for variability and imprecision in sample estimates that often accompany smaller pilot studies, we will create 95% confidence intervals (CIs) around all feasibility and acceptability outcomes and consider the data supportive of progression to a full trial if these confidence intervals include our metric for success.

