Specific Aim 1: Evaluate the acceptability of the EMPOWER intervention, as indicated by treatment engagement and participant reported treatment credibility and satisfaction, and potential for treatment efficacy. We will examine treatment engagement at each session and will measure

Table 2. Study Measures

Variable	Measure	Time-Point (Month)		
		0	4	8
Participant Engagement	Treatment Engagement Ques.	Every session		
Treatment Credibility	Credibility/Expectancy Scale	X		
Treatment Satisfaction	CSQ-8		X	X
Qualitative Evaluation	Qualitative Interview			X
Pain Impact	RTF Impact Stratification	X	X	X
Body Weight	By Digital Scale	X	X	X
Intensity, Interference, Phys. Function	PROMIS Pain Measures	X	X	X
Functional Performance	BPS	X		X
Back-Related Disability	RMDQ	X	X	X
Physical Activity	IPAQ	X	X	X
Pleasant Activity Engagement	Self-Reported Engagement	X	X	X
Reward from Activities	MAPA	X	X	X
Positive Affect	PANAS	X	X	X
EMA of Pain Intensity	Smartwatch Ratings	X		X
EMA of Mood and Physical Activity	Smartwatch Ratings	X		X
Quality of Life	WHOQol Bref	X	X	X

Note: Ques=Questionnaire; Phys=Physical. See text for a full description of abbreviations for study questionnaires.

several aspects of global acceptability at baseline and at the 4- (mid-intervention) and 8-month (end of intervention) assessment period.

Session-level Engagement. Treatment engagement will assess participants' effort exerted during group activities/phone calls (using a 9-point Likert rating scale), completion of homework (yes/no), and engagement in group and individual discussions (using a 9-point Likert rating scale). Responses will be examined after sessions and after all four cohorts are complete (considering the mean and range of Likert ratings for each questionnaire item). We will also develop a 95% CI around the Likert ratings and examine if our metric for success falls within that interval (i.e., ≥ 6 on a 9-point Likert scale).

Global Treatment Engagement. The mean portion of group and phone sessions attended will be examined across the entire sample, as well as trends in the portion of sessions attended across the four cohorts. We will determine if our metric for success falls within a 95% CI around our identified threshold for success. The percentage of participants who complete $\geq 80\%$ of group and phone sessions combined will also be measured, as well as the portion who complete $\geq 70\%$ of group sessions and $\geq 70\%$ of phone sessions (considered separately).

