Global Treatment Satisfaction and Credibility. On the Client Satisfaction Questionnaire-8 (CSQ-8) and on the adapted Treatment Credibility and Expectancy Scale, we will present the mean (sd) and range as well as develop a 95% CI around questionnaire ratings to examine in relation to our metric for success (i.e., treatment satisfaction: ≥ 3 on a 4-point Likert scale; treatment credibility: ≥ 7 on a 11-point Likert scale).

Potential for Efficacy. To evaluate the potential for intervention efficacy on pain impact, weight, and key putative mediators, we will determine the mean, standard deviation, and range associated with treatment-related changes in these outcomes. We will also develop 95% CIs around the observed mean and examine whether a pre-determined minimal change score is within these CIs. For pain impact, the minimally important change score will be 30% of the baseline score as this number has been previously defined as a clinically meaningful reduction in pain.¹⁹ For weight, the minimal important change score is a 5% reduction in body weight, given that this value is well-established to result in clinically important changes in health parameters.³¹

Specific Aim 2: Determine trial feasibility, including the ability to meet pre-specified recruitment and retention metrics.

Recruitment. We will present the rate of recruitment in units of participants/week (only including weeks of active recruitment). We will also report the portion of participants contacted and screened, including those who were enrolled and reasons for ineligibility. We will develop 95% CIs around the recruitment rate and determine if our metric for success is within that confidence interval (i.e., ≥ 2.5 participants enrolled per week during active recruitment; $\geq 90\%$ of those who enroll commence treatment).

Retention. We will present the portion of participants who attend the 4- and 8-month assessment sessions, by cohort and the total sample. We will determine if our metric for successful retention ($\geq 80\%$ who enroll complete the 8-month assessment, among the final two cohorts) falls within a 95% CI of our obtained retention.

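### A minimum target counts as satisfied whenever the 95% CI includes it, so observed retention of about 62-67% would satisfy the 80% minimum (assuming 24 in the final two cohorts)

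*Combined protocol and SAP*

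**What the plan says.** The general rule is in section 6, Research Plan, under Statistical Methods. To allow for the imprecision of a small pilot, the investigators will put 95% CIs around the feasibility and acceptability outcomes and "consider the data supportive of progression to a full trial if these confidence intervals include our metric for success".

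The rule is then repeated outcome by outcome:

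- **Session-level Engagement** (target at least 6 on a 9-point scale): "examine if our metric for success falls within that interval".
- **Recruitment** (at least 2.5 enrolled per week; at least 90% of those enrolled start treatment): "determine if our metric for success is within that confidence interval".
- **Retention** (at least 80% of those enrolled complete month 8): the metric is checked "among the final two cohorts) falls within a 95% CI of our obtained retention".
- **Satisfaction** (at least 3 of 4) and **credibility** (at least 7 on an 11-point scale) are compared with their targets through a CI and fall under the general rule.

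Attendance is worded differently. "The mean portion of group and phone sessions attended will be examined across the entire sample", and the check is whether the "metric for success falls within a 95% CI around our identified threshold for success". No target is given for mean attendance, or for the percentage of participants reaching the 80% or 70% session-completion levels.

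On reporting, the Retention paragraph states: "We will present the portion of participants who attend the 4- and 8-month assessment sessions, by cohort and the total sample".

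**The concern.** Each target is a floor. Whether an interval includes the floor answers a different question: whether the data rule it out. With few participants the interval is wide and rules out little, so an estimate well below the floor still passes. The rule rewards imprecision.

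This is the plan's stated test of whether the pilot supports a larger trial. A pilot that fell well short of its own minimum would get the same verdict as one that reached it. The verdict alone could not separate a pilot that is ready to proceed from one whose retention procedures need changing first.

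Two wording problems accompany this:

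- Taken literally, an interval lying wholly above the metric does not include it, so excellent retention would fail. Reading the metric as a region (80% or more) removes this.
- For attendance, the interval is placed around the threshold instead of around the observed result, and no threshold is stated. That check cannot be carried out as written.

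**Working it through.** **Inputs.** Retention target 80%, judged in the final two cohorts (Retention). Four cohorts (Session-level Engagement). Enrolment: "a total of 48 participants to be recruited for study intervention procedures (we anticipate recruiting a total of 60 people" (Participants). The plan's figure reproduces: 40 + 20% of 40 = 40 + 8 = 48. *Assumption:* equal cohorts, so 48/4 × 2 = 24 in the final two. The CI method is not named, so several are tried, all two-sided 95%.

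**Lowest passing count at n = 24** (smallest x whose upper limit reaches 0.80):

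- Wald: p + 1.96·√(p(1−p)/n). At 15/24: 0.625 + 1.96·√(0.625 × 0.375/24) = 0.625 + 1.96 × 0.0988 = 0.819, pass. At 14/24: 0.781, fail.
- Exact (Clopper-Pearson): the 97.5% quantile of Beta(x+1, n−x). At 15/24: CI 40.6-81.2%, pass. At 14/24: upper limit 77.9%, fail.
- Wilson: [p + z²/2n + z·√(p(1−p)/n + z²/4n²)] / (1 + z²/n). At 16/24: (0.7467 + 0.2049)/1.1601 = 0.820 (CI 46.7-82.0%), pass. At 15/24: upper limit 78.8%, fail.
- Agresti-Coull and Jeffreys: 16/24.

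The lowest pass is therefore 62.5% or 66.7%. At 15/24, 9/24 = 37.5% are lost, against the 20% attrition assumed under Participants.

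**Other denominators:**

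| n | exact | Wilson |
|---|---|---|
| 20 | 12 (60.0%) | 13 (65.0%) |
| 24 | 15 (62.5%) | 16 (66.7%) |
| 28 | 18 (64.3%) | 19 (67.9%) |
| 30 (if 60 count as enrolled) | 19 (63.3%) | 20 (66.7%) |
| 48 | 33 (68.8%) | 33 (68.8%) |

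**Chance of satisfying the retention metric at n = 24**, from binomial upper tails P(X ≥ 15), P(X ≥ 16) and, for an estimate of at least 80%, P(X ≥ 20), because 19/24 = 79.2%:

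| True retention | exact | Wilson | estimate ≥ 80% |
|---|---|---|---|
| 60% | 49% | 33% | 1% |
| 65% | 69% | 53% | 4% |
| 70% | 85% | 72.5% | 11% |

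For 20 to 30 participants in the final two cohorts, across all five methods, the pass chance is 46-76% at true 65% and 68-89% at true 70%.

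**Starting treatment (at least 90%).** The denominator meant by enrolment is not defined. With 48, the lowest pass is 39/48 = 81.3% (exact), 40/48 = 83.3% (Wilson) or 38/48 = 79.2% (Wald). With 60, it is 49/60 = 81.7%, 50/60 = 83.3% or 48/60 = 80.0%.

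**Literal reading.** At 24/24 the exact lower limit is 0.025^(1/24) = 0.858. The interval 85.8-100% does not include 80%.

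**The case against.** The best defence is that the leniency is deliberate and disclosed. A pilot of this size should not be stopped by a strict test, and the plan says it is allowing for imprecision. Retention strategies may be adjusted during the pilot, retention is judged in the final two cohorts after any such changes, and observed figures are reported by cohort and in total, so a reader would see a shortfall. The general rule also refers to the CIs of all the outcomes; if every one must include its metric, the chance of an overall favourable verdict is lower than the one-metric chances above. Finally, the fall in the bar with sample size is not smooth: the exact bar is 64.3% at 28 but 63.3% at 30, and the Wilson bar is 66.7% at both 24 and 30.

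Much of this stands as qualification. The probabilities are for one metric, the report would show the shortfall, and within 20 to 30 participants the bar moves in integer steps; the dependable statement is that it is lower there than at 48. None of it repairs the rule. Allowance for imprecision justifies an uncertain category, not calling a shortfall support. Requiring every metric to pass leaves the fault in each one.

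**Conclusion.** The concern holds. As written, the progression rule treats failure to exclude a minimum as support. For retention, an observed 62.5% (exact, Wald) or 66.7% (Wilson, Agresti-Coull, Jeffreys) would satisfy an 80% target. At true retention of 65% the metric passes 69% (exact) or 53% (Wilson) of the time, against 4% if the estimate had to reach the target.

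These figures rest on 24 participants in the final two cohorts, which the plan does not state, and on the choice of CI method. For the sizes tabulated from 20 to 30 the bar stays between 60.0% and 67.9%, so the conclusion does not depend on either. The point should be fixed before the criterion is applied; it affects the verdict drawn, not the data collected.

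**What to change.** Replace the inclusion rule, for each metric with a stated target (engagement, satisfaction, credibility, recruitment rate, starting treatment, retention), with three levels:

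- **Met:** estimate at or above the target, including any CI wholly above it.
- **Uncertain:** estimate below the target, but the 95% CI reaches it. Report as not met; it supports progression only with changes stated in the report.
- **Not met:** whole 95% CI below the target.

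Put the attendance CI around observed attendance and state the target it is compared with. In the same edit, name the CI method, define the enrolment denominator and say how the metrics combine. Keep the final-two-cohort retention metric, with the planned total-sample figure beside it.

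The cost is protocol wording; no extra participants or data are needed. With the same CI method, and reading each target as a minimum, met plus uncertain is exactly the set that passes today, so no result turns from go to stop.

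The price is that good retention will often be labelled uncertain. At n = 24 (exact / Wilson):

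| True retention | met | uncertain | not met |
|---|---|---|---|
| 65% | 4% | 64% / 48% | 31% / 47% |
| 80% | 46% | 53% / 50% | 1% / 4% |
| 90% | 91% | 9% | under 0.1% |

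### The attendance success rule puts its 95% CI around the threshold instead of observed attendance, gives no target number, and does not say whether the 8 optional group sessions count

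*Combined protocol and SAP*

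**What the plan says.** The Statistical Methods paragraph sets a general rule in two parts. The first says where the intervals go: "we will create 95% confidence intervals (CIs) around all feasibility and acceptability outcomes." The second says how they bear on the decision, namely that the investigators will "consider the data supportive of progression to a full trial if these confidence intervals include our metric for success." Specific Aims 1 and 2 then apply it outcome by outcome.

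For attendance, Global Treatment Engagement says: "The mean portion of group and phone sessions attended will be examined across the entire sample." The decision sentence is: "We will determine if our metric for success falls within a 95% CI around our identified threshold for success." No value follows. The paragraph goes on to list, as further measurements, the percentage of participants who complete at least 80% of group and phone sessions combined, and the portions who complete at least 70% of each type.

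Intervention Procedure describes 8 core group sessions, 8 optional group sessions and 8 phone calls. Group sessions run every other week, with calls in the weeks between. Section 5 allows a 4-month form of the intervention for those who complete the core sessions only. Qualitative Interviews and Treatment Outcome and Mediator Measures also provide for such participants.

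**The concern.** Statistical Methods makes acceptability outcomes part of the case for a full trial, and Specific Aim 1 names treatment engagement first among the acceptability indicators. The attendance rule should therefore return an answer.

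Read literally, it cannot. A threshold has no sampling error, so an interval around it has no clear meaning. The quantity tested against that interval is the metric, not the observed mean. If metric and threshold are the same number, the check passes whatever attendance turns out to be.

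Moving the interval to the observed mean does not finish the job, because there is still no target to compare it with. The denominator is also open. If optional sessions count as missed when not taken, adherence is understated for people following a course that the protocol accepts, and the same attendance record supports two quite different figures.

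**Working it through.** **Step 1. Where each rule places its interval, and what number it states.** All rows come from Specific Aims 1 and 2.

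| Outcome | Interval placed around | Stated metric |
|---|---|---|
| Session-level engagement | observed ratings: "develop a 95% CI around the Likert ratings and examine if our metric for success falls within that interval" | at least 6 on a 9-point scale |
| Satisfaction; credibility | observed ratings: "develop a 95% CI around questionnaire ratings to examine in relation to our metric for success" | at least 3 on a 4-point scale; at least 7 on an 11-point scale |
| Recruitment | observed rate: "develop 95% CIs around the recruitment rate and determine if our metric for success is within that confidence interval" | at least 2.5 per week; at least 90% of enrollees start treatment |
| Retention | observed retention: "falls within a 95% CI of our obtained retention" | at least 80% at 8 months, final two cohorts |
| Mean attendance | the threshold | none |

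Attendance is the odd one out in both columns. The 80% and 70% figures do not fill the gap: they classify individual participants, they are listed as additional measurements, and no target share of participants is attached to them.

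**Step 2. The possible denominators.** Inputs from Intervention Procedure: 8 core groups, 8 optional groups, 8 calls.

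- Core groups plus calls: 8 + 8 = 16.
- All groups plus calls: 16 + 8 = 24.

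**Step 3. Call timing.** The protocol does not say how many calls fall in the core phase. At the stated alternating pace, 8 group weeks and 8 call weeks fill 16 weeks, which fits the 4-month core. Calls throughout 16 fortnightly groups (32 weeks) would number 16, not the stated 8. I therefore assume that all 8 calls fall in the core phase.

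**Step 4. One participant who attends every core group and every call, and no optional session.**

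| Measure | Optional sessions counted | Not counted | Completion cut-off |
|---|---|---|---|
| Group | 8/16 = 50% | 8/8 = 100% | 70% |
| Combined | 16/24 = 66.7% | 16/16 = 100% | 80% |
| Phone | 8/8 = 100% | 8/8 = 100% | 70% |

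In sessions, the 70% group cut-off is 0.70 × 16 = 11.2, so 12 of 16, or 0.70 × 8 = 5.6, so 6 of 8. The 80% combined cut-off is 0.80 × 24 = 19.2, so 20 of 24, or 0.80 × 16 = 12.8, so 13 of 16. This participant attends 8 groups and 16 sessions in all, and so misses both cut-offs on one count and meets both on the other.

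The 50% group figure does not depend on call timing. The 66.7% combined figure is a maximum, so it stays below 80% even if the assumption in Step 3 is wrong.

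The protocol states no attendance figure, so there is none to reproduce.

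**The case against.** The strongest reply is that a reasonable analyst would know what to do. Statistical Methods already says where the interval goes, so the attendance sentence is a slip of wording. The text also leans toward a core-only denominator: the extra sessions are called optional, Section 5 describes a 4-month form, the interviews of completers include people who took the core sessions only, and the reference to 16 sessions there serves only to time the interview. The study is an exploratory single-arm pilot, and Data and Safety Monitoring mentions a Manual of Procedures that might hold the target.

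Much of this stands. The intended interval placement is clear. It remains true that the sentence states a different rule, that the protocol gives no number, and that a lean toward one denominator is not a definition.

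Several stronger readings are tempting and are not supported:

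- *Attendance is the only outcome without a target.* It is not. Homework completion and the 80% and 70% completion shares have none either. Attendance is the only one with its own success-metric sentence and no number.
- *A progression cut-off is breached, or the session ratings are affected.* Neither follows. The 80% and 70% items are not progression criteria, and the rating metric has its own number and a correctly placed interval.
- *Phone attendance also falls below its cut-off.* That needs a slower call pace than the protocol states.
- *The sample mean would drop by 100 − 66.7 = 33.3 points.* Among otherwise full attenders, that needs every participant to be core-only, and no core-only share is given.
- *The target will be chosen after the results are known.* The text leaves that possible but does not show it.

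**Conclusion.** The point holds in this form. The attendance rule is wrong as written, because its interval surrounds a fixed threshold, contrary to the plan's own general rule and to every parallel rule. It also lacks the number that would let it work once the interval is moved, and it leaves the standing of the 8 optional sessions open.

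The size can be given for an individual only: 50% against 100% of group sessions, and 66.7% against 100% combined, for a fully adherent core-only participant. The combined figure assumes that all 8 calls fall in the core phase. No effect on the sample mean is claimed. This should be fixed: it concerns a stated input to the progression decision, and the repair is small.

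**What to change.** Replace the decision sentence with wording such as: *We will compute a 95% CI around the observed mean proportion of sessions attended and regard the result as supportive if that interval includes, or lies above, a target of at least X%.* The investigators set X before attendance data are examined.

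State openly that the words about lying above the target are a deliberate clarification. Statistical Methods speaks only of inclusion, so an interval wholly above the target would literally fail. Apply the same clarification to the other at-least metrics.

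Use one fixed denominator for every participant: the 8 core group sessions plus the calls scheduled in the core phase, with that number of calls stated. Participants who drop out keep the full denominator, so dropout still counts as missed sessions. Do not use a denominator based on the course each participant ended up taking, because it would depend on behaviour after baseline.

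Report uptake of the 8 optional sessions, and attendance over all 16 groups plus 8 calls, separately as descriptive results.

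The cost is a few sentences of protocol text and one extra tabulation of data already collected.
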